Urothelial cancer (UC) represents the fourth most frequently diagnosed tumor worldwide, accounting for nearly half a million of new cases annually [1,2]. Despite approximately the 70% of patients present with non-muscle invasive UC, more than one fourth of cases are diagnosed with advanced or metastatic disease, and systemic treatments remains the only therapeutic option [3,4]. Cisplatin-based chemotherapy is the standard first-line treatment in metastatic UC (mUC), with these regimens reporting a median survival of approximately 15 months and a 5-year survival rate of 15%, according to landmark registration trials [5,6]. Nonetheless, since the majority of patients with metastatic disease are over 65 years old, a substantial proportion is not deemed eligible for platinum-based chemotherapy, due to concomitant comorbidities [7,8]. In addition, disease progression inevitably occurs following the front-line treatment, and the prognosis of these patients remains poor [9,10].

The advent of modern immunotherapy and immune checkpoint inhibitors (ICIs) has recently revolutionized the treatment landscape of cancer patients in recent years [11,12]. ICIs targeting programmed cell death protein-1 (PD-1), programmed cell death ligand 1 (PD-L1), and cytotoxic T-lymphocyte antigen 4 (CTLA-4) are able to enhance T-cell mediated anti-tumor responses, resulting in improved clinical outcomes in several hematological and solid tumors [13,14]. Phase III clinical trials evaluating the role of immunotherapy in mUC patients have reported

The ARON PROJECT

Global experiences, perspectives and access to cure in patients with genitourinary tumors

important results, as also witnessed by the approval of five ICIs by the United States Food and Drug Administration (FDA) in the last few years: the PD-1 inhibitors, pembrolizumab and nivolumab, and the PD-L1 inhibitors atezolizumab, avelumab, and durvalumab [15,16]. However, only a small subset of advanced-stage UC patients may benefit from immunotherapy reaching a durable response. Antibodies–drug conjugates such as enfortumab vedotin, directed against nectin-4, and sacituzumab govitecan, directed against Trop-2, have been compared with standard chemotherapy in two randomized clinical trials including patients with locally advanced or mUC who had previously received platinum-based treatment and subsequently PD-1 or PD-L1 inhibitor. Both drugs shown to significantly improve survival compared to chemotherapy [17,18]. This led to the FDA approval of enfortumab vedotin for advanced-stage UC patients who had previously received PD-1 or PD-L1 inhibitor and platinum-containing chemotherapy, or who are ineligible for cisplatin-containing chemotherapy and had previously received one or more lines of systemic therapy [17,19].

With the emerging therapeutic options available, there is an urgent need for the identification of predictive biomarkers of response to ICIs, as well as a deeper understanding the role of immunotherapeutic agents in mUC [20]. Recently, several emerging studies aimed to evaluate biomarkers and predictors of response in this setting, including protein markers, immune-related cells, genetic markers, and host-related factors [21–22]. Regarding the latter, only a few studies

have investigated the putative predictive value of routinely assessed clinico-pathological data, including age, gender, liver metastases, and histological features.

The ARON-2 Study has been designed to share and analyze the global real world experiences with the use of pembrolizumab as first and second line and enfortumab vedotin for mUC aimed to analyze the efficacy and safety of these therapeutic approaches in specific subpopulations and to investigate for the presence of prognostic factors in this context.

2. Study Design and Endpoints

The ARON-2 Study is designed as an International Multicentric Retrospective Study to collect global experiences with the use of pembrolizumab and enfortumab vedotin used in different settings in patients with metastatic UC (mUC).

2.1 Primary End-Point

- To analyze real-world data on the efficacy and safety of pembrolizumab and enfortumab vedotin in patients with mUC.

2.2 Secondary End-Points

- To apply artificial intelligence technology to the study of real-world data for clustering and Artificial Neural Network analyses

The ARON PROJECT

Global experiences, perspectives and access to cure in patients with genitourinary tumors

- To assess the prognostic role of smoking attitude, obesity, age, renal insufficiency, primary tumor location, histology and concomitant medication in patients treated with pembrolizumab and/or enfortumab vedotin
- To compare different therapeutic sequences in mUC patients

2.3 Evaluation of the Endpoints

- Overall Survival (OS) will be defined as a time from the start of the therapy until death from any cause
- Progression-Free Survival (PFS) will be defined as a time from the start of the therapy until progression or death from any cause. Patients switched to the following line of treatment without progression or lost at follow-up at the time of analysis were censored at their last follow-up date
- Radiological assessment was performed according to the RECIST 1.1 criteria [23] and the data on objective response (complete regression=CR, partial regression=PR, stable disease=SD or progressive disease=PD) will be collected and analyzed
- The Overall Response Rate (ORR) and Disease Control Rate (DCR) will be defined as the rates of CR + PR and CR + PR + SD, respectively (according to the RECIST 1.1 criteria) [23]
- Treatment related adverse events (e.g., cutaneous toxicity, neurological toxicity and hyperglycemia/mellitus diabetes) will be assessed according to

The ARON PROJECT

Global experiences, perspectives and access to cure in patients with genitourinary tumors

the Common Terminology Criteria for Adverse Events (CTCAE) v 5.0 [24].

Grade ≥ 3 adverse events will be analyzed with a special focus

3. Study Population

The ARON-2 study retrospectively analyze patients treated with pembrolizumab, as first-line therapy in platinum-unfit patients or as second-line therapy in patients progressed after previous platinum-based chemotherapy, and/or enfortumab vedotin, as third-line therapy in patients previously treated with platinum-based chemotherapy and subsequently with PD-1 or PD-L1 inhibitor.

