3.3 Estimated Enrollment

In order to determine the minimum sample size for the purpose of the analysis on patients treated by pembrolizumab, we identified the smallest subpopulation among the planned sub-analyses, which was represented by obese patients with advanced UC. According to the literature, the incidence of obesity can be estimated at 30% in patients with UC [21]. In the study that led to the FDA approval of Pembrolizumab in UC patients [15], the median OS in the standard control arm with chemotherapy was 7.4 months, with a hazard ratio of 0.73. In our study, we set a significance level of 0.05 and the power to 80% for a minimal observation time of 12 months [22,25]. Under these conditions, we estimated an enrollment of 110 obese UC patients, in order to expect to observe at least 78 events in this group, which corresponds to an estimated overall study population of 367 patients affected by advanced UC.

In the study that led to the FDA approval of enfortumab vedotin in UC patients [17], the estimated percentage of patients alive at 12 months was 51.5% (95% CI, 44.6 to 58.0) in the enfortumab vedotin group and 39.2% (95% CI, 32.6 to 45.6) in the chemotherapy group with a delta of 12.3 among the two groups. In this study,

The ARON PROJECT

Global experiences, perspectives and access to cure in patients with genitourinary tumors

we tested the hypothesis that, using the enfortumab vedotin in clinical practice, OS would reach at least 60% after 12 months from the start of therapy. Study plan will include at least 361 patients with an estimated drop out of 10–15%. It was calculated that a minimum of 311 evaluable patients should be enrolled with an α of 0.05 and a β of 0.80 (STATASOFT).

4. Statistical Analysis and Data Collection

PFS and OS will be estimated by Kaplan-Meier method with Rothman's 95% confidence intervals (CI) and compared by using the log-rank test. Univariate and multivariate analyses will be performed by using Cox proportional hazards models. The chi-square test will be used to compare categorical end-points. Significance levels will be set at a 0.05 value and all p values will be two-sided. The statistical analysis will be performed using MedCalc version 19.6.4 (MedCalc Software, [name]).

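### PFS of patients who switch line without progression is censored at last follow-up rather than at the switch, so time on the next drug enters PFS on the study drug

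*Protocol*

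**What the plan says.** Protocol section 2.3 defines PFS as the "time from the start of the therapy until progression or death from any cause". The next sentence gives the censoring rule: "Patients switched to the following line of treatment without progression or lost at follow-up at the time of analysis were censored". The date is the same for both groups, who "were censored at their last follow-up date". The protocol does not define that date. It names neither the switch nor the last tumour assessment before it as the censoring date.

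Three other places bear on the point:

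- OS, also in section 2.3, is the "time from the start of the therapy until death from any cause", so patients are followed past a change of treatment.
- Section 2.2 lists as a secondary end-point "To compare different therapeutic sequences in mUC patients", so later lines are part of the data.
- Section 4 states how PFS is used: "PFS and OS will be estimated by Kaplan-Meier method with Rothman's 95% confidence intervals (CI) and compared by using the log-rank test". Cox models follow.

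**The concern.** There are two coherent ways to treat a patient who starts another drug before progression. One censors because of the switch, at the switch or at the last assessment before it. The other ignores the switch and counts progression or death whenever it occurs. Section 2.3 takes its reason for censoring from the first and its date from the second.

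Take a patient who leaves pembrolizumab at month 4, starts the next drug and is last seen at month 20. On the literal rule this patient contributes 20 progression-free months, 16 of them on another drug, and cannot have an event in those 16 months. The denominator of the Kaplan-Meier estimate then holds patients who cannot enter the numerator, and PFS is overstated.

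PFS is one of the efficacy measures behind the primary end-point in section 2.1. It is also an outcome that may be compared across prognostic factors and treatment sequences. If switching without progression is more common in one group, that group will appear to have longer PFS.

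**Working it through.** No figure in the protocol depends on the PFS rule, since both sample sizes in section 3.3 rest on OS. There is nothing to reproduce, so the check shows how the rule behaves under assumed inputs.

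**Assumed inputs (none is in the protocol).** True PFS is exponential with median 4 months. A fraction *f* of patients (5, 10 or 20%) switches before progression, independently of prognosis. Time from switch to last follow-up is exponential with mean *m* of 6 to 10 months.

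**Formula, literal reading.** Let λ = ln 2 / 4 = 0.1733 per month, σ = λf/(1 − f) be the switch rate, and μ = 1/m.

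- Unswitched and event-free at *t*: N(t) = exp(−(λ+σ)t).
- Switched and still in the risk set at *t*: W(t) = σ/(λ+σ−μ) × [exp(−μt) − exp(−(λ+σ)t)].
- Only the first group can have an event, so the Kaplan-Meier estimate follows the hazard h(t) = λN/(N+W), and estimated PFS is exp(−∫h).

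**Numbers put in.**

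- *f* = 10%, *m* = 6: σ = 0.0193. At 12 months N = 0.0992 and W = 0.0269, so h is 0.0992/0.1261 = 79% of the true hazard.
- *f* = 20%, *m* = 10: σ = 0.0433. At 12 months N = 0.0743 and W = 0.0843, so h is 47% of the true hazard. More than half of those counted at risk are switchers who cannot have an event.

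| Switching | Median PFS, months (true 4.0) | 12-month PFS (true 12.5%) |
|---|---|---|
| 5% | 4.08 | 14.0 to 14.5% |
| 10% | 4.16 to 4.18 | 15.7 to 16.7% |
| 20% | 4.40 to 4.44 | 19.9 to 22.0% |

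Ranges are over *m* from 6 to 10 months. Censoring at the switch gives the true values under these assumptions.

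**Other inputs.** A simulation used true medians of 3 or 6 months, 5 to 30% switching, follow-up uniform from 12 to 30 months and an unchanged hazard after the switch. The literal rule raised the median by about 2% (3.00 to 3.06) to 26% (3.00 to 3.78). It raised 12-month PFS by about 2 points (24.8 to 26.7%) to 23 points (6.2 to 29.4%). Censoring at the switch and counting all later events both recovered the truth.

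**Log-rank level.** This was simulated with no true PFS difference, a mean of 8 months after the switch, and 110 v 257 patients (section 3.3: 110 obese of 367, and 367 − 110 = 257). The nominal level is 5%.

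| Switching in the two groups | Rejection, literal rule |
|---|---|
| Equal (10% v 10%, 20% v 20%) | about 5% |
| 15% v 10% | 8 to 9% |
| 20% v 10% | 20% |
| 25% v 10% | 37 to 40% |

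Censoring at the switch gives 4 to 6% in the unequal cases.

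**When the switch is itself an unrecorded progression.** Suppose 15% of progressions are charted only as a switch. The literal rule then gives a median of about 5.0 months and 12-month PFS of about 22%. Censoring at the switch still gives 4.7 months and 17%. So (4.7 − 4.0)/(5.0 − 4.0) = 70% of the median shift, and (17 − 12.5)/(22 − 12.5) = 47% of the 12-month shift, come from informative censoring and not from the censoring date.

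**The case against.** The strongest reply is that the sentence can be read another way. The words about the time of analysis may govern both groups, so that only switchers still event-free at analysis are censored and later progressions and deaths count. That is ordinary follow-through PFS, and under an unchanged hazard it gives the true curve. Last follow-up might also have been meant as the last assessment before the switch. Neither reading is stated, and the figures above belong to the literal one. Under the follow-through reading the loss of events falls away, but next-line time is still part of PFS on the study drug. Centres abstracting charts need to know which is meant.

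A reader might infer several stronger things that the protocol does not support:

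- *That the rule contradicts the PFS definition, which counts every death.* A censoring rule qualifies an event definition. Censoring at the switch also leaves out later deaths, so the fault lies in the date.
- *That any factor or sequence linked to having a next line will show longer PFS, or that PFS tests generally lose their 0.05 level.* A next line begun after progression is untouched, because the event has already occurred. The level moves only when rates of switching without progression differ between groups.
- *That the whole shift from unscanned progressions is due to this rule.* Most of the median shift would remain after re-dating.

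It is also fair that no switch rate is given, and that at 5% switching the median moves by less than 0.1 month.

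**Conclusion.** The point holds as a defect in a stated rule, not as a gap that a statistical analysis plan would fill. The protocol fixes a date for switchers that normally lies after the start of the next drug, and on either reading of the sentence next-line time enters PFS.

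On the literal reading the bias is upward. It is small if few patients switch and material on 12-month PFS at 10 to 20% switching (about 16 to 22% against a true 12.5%, with the assumed 4-month median and 6 to 10 months of follow-up after the switch). These sizes rest on assumed inputs and on switching independent of prognosis. Comparisons are affected only through unequal rates of switching without progression.

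OS, the sample sizes and every figure stated in the protocol are untouched. For that reason, and because the switch rate is unknown, this is something that should be fixed rather than a flaw that undermines the study.

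**What to change.** In section 2.3, keep the present wording for patients lost to follow-up and replace the switcher half with:

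> Patients who start a following line without documented progression are censored at the last tumour assessment on or before the start of that line (or at that start date if the assessment date is not available); no time after that start counts towards PFS.

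This still assumes that switching says nothing about impending progression. Add one sensitivity analysis in which the start of the next line counts as an event (time to next treatment or death), to cover switches made for progression that was never scanned.

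The cost is one sentence and one extra analysis. Reported PFS will be somewhat shorter. Section 4 lists treatments among the data collected but names neither next-line start dates nor tumour-assessment dates. The sponsor should confirm that the start date is captured; the fallback in the sentence covers a missing assessment date.

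### PFS for patients who switch line without progression is censored at last follow-up instead of at the switch, so next-line time is credited to the study drug

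*Protocol*

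**What the plan says.** Protocol section 2.3 first defines PFS: it "will be defined as a time from the start of the therapy until progression or death from any cause". The next sentence sets the censoring rule. It says that patients moved to the "following line of treatment without progression or lost at follow-up at the time of analysis were censored at their last follow-up date". The rule thus names two groups, switchers without progression and patients lost to follow-up, and gives both the same date. Neither the date of the switch nor the last assessment before it is named as a censoring date, and no other section corrects this.

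The same section defines OS as the "time from the start of the therapy until death from any cause", so follow-up continues beyond the end of study treatment. Section 4 puts PFS into the main analyses: "PFS and OS will be estimated by Kaplan-Meier method", with log-rank tests and Cox models. Section 2.2 adds the aim "To compare different therapeutic sequences in mUC patients" and the study of prognostic factors such as age, obesity and renal insufficiency.

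**The concern.** A patient who leaves the study drug without progression, for example because of toxicity, can be handled coherently in two ways. PFS can stop at the switch, or it can run through the switch with later progression or death counted as an event. Taken literally, the written rule does neither. It keeps the time after the switch and discards the events in that time.

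PFS is one of the efficacy measures behind the primary objective. It is also compared across subgroups and possibly across treatment sequences. If switching without progression is more common in one group than another, for example in older patients or those with renal insufficiency, the distortion is differential and could create or hide a difference. Several manuscripts are planned from data supplied by many centres, so an ambiguous rule could also be applied differently to similar patients.

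**Working it through.** **No plan figure to reproduce.** Both calculations in section 3.3 rest on OS. No sample size, event count or power figure depends on PFS.

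**One switcher under each rule.** Let the switch occur at time W, progression on the next line at P and death at D, with W < P < D, all before the analysis.

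| Rule | PFS time | Status |
|---|---|---|
| Censor at the switch | W | censored |
| Written rule, literal reading | D (last follow-up) | censored |
| Written rule, second reading | P | event |

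The literal reading gives the longest time and no event, although the preceding sentence makes both P and D events. On the second reading, absence of progression at the time of analysis qualifies both groups, so only switchers still event-free are censored. The interval from W onward is still attributed to the study drug.

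**Size, first illustration.** All inputs are assumptions: exponential times, median post-switch follow-up 8 months, staggered cut-off at 12 to 36 months, 200,000 simulated patients per scenario. With median m, true 12-month PFS is 0.5^(12/m): 0.5^3 = 12.5% for m = 4 and 0.5^2 = 25% for m = 6.

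| Median PFS (months) | Share switching | 12-month PFS, literal rule | Excess (points) |
|---|---|---|---|
| 4 | 5% | 14.5% | 2.0 |
| 4 | 10% | 17.0% | 4.5 |
| 4 | 20% | 22.5% | 10.0 |
| 6 | 5% | 26.5% | 1.5 |
| 6 | 10% | 28.2% | 3.2 |
| 6 | 20% | 31.6% | 6.6 |

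For m = 4 the reported median becomes 4.1, 4.2 and 4.4 months instead of 4.0.

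**Size, second illustration.** 400,000 patients per scenario, m = 5, the same cut-off range. Survival after the switch is exponential with median 7.4/0.73 = 10.1 months, using the OS figures in section 3.3. The progression hazard on the next line is assumed equal to that on the study drug, with the death hazard added. Cells show median in months and 12-month PFS.

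| Share switching | Censored at switch | Literal reading | Second reading |
|---|---|---|---|
| 5% | 5.0; 19.0% | 5.1; 20.8% | 4.9; 18.4% |
| 10% | 5.0; 19.0% | 5.2; 22.9% | 4.9; 18.0% |
| 20% | 5.0; 18.9% | 5.6; 27.5% | 4.8; 16.7% |
| 30% | 5.0; 18.9% | 6.1; 33.2% | 4.7; 15.6% |

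**Check by formula.** If every switcher stayed in the risk set past month 12, the literal estimate would reach a ceiling of 1 − (1 − p)(1 − 0.5^(12/(m(1 − p)))), where p is the share switching. For m = 5 and p = 0.20 this is 1 − 0.80 × (1 − 0.5^3) = 1 − 0.80 × 0.875 = 30.0%. For p = 0.10 it is 1 − 0.90 × (1 − 0.1575) = 24.2%. The simulated 27.5% and 22.9% lie just below, as they should, because some switchers die before month 12 and leave the risk set.

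**Which next line?** The enfortumab vedotin criterion in section 3.1 requires progression on earlier platinum chemotherapy and on a PD-1/PD-L1 inhibitor. A patient who enters that cohort after progressing on pembrolizumab already has a pembrolizumab PFS event. The introduction to section 3 is looser and speaks only of previous treatment with such an inhibitor.

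**The case against.** The strongest reply is that the two sentences can be reconciled. If only switchers still event-free at analysis are censored, later progression or death counts, the conflict with the definition disappears, and the second illustration shows PFS slightly lower, not higher. This stands: the dropped events and the upward bias belong to the literal reading. It does not rescue the sentence, which supports both readings and credits next-line time to the study drug under either.

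A reader might infer that pembrolizumab PFS is broadly contaminated by time on enfortumab vedotin. The documents do not support that. Section 3.1 limits enfortumab vedotin to patients who have progressed on a PD-1/PD-L1 inhibitor, so most of that sequence is untouched. What remains is switching to other therapies, and any patient admitted under the looser wording of section 3.

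The switch rates, PFS medians and post-switch follow-up are all assumed, and with few switchers the effect is small. That also stands. Both illustrations let switching be unrelated to prognosis, which is why censoring at the switch recovers the true curve. Switching for toxicity or deterioration may be informative, so the replacement rule is not free of bias either.

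Finally, sensitivity analyses and assessment-based censoring for patients lost to follow-up are often left to a statistical analysis plan. Their absence is not the point here. The point is that the Protocol states a rule for switchers, and the stated rule is wrong or at best ambiguous.

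**Conclusion.** The concern holds in a conditional form. Section 2.3 gives switchers a censoring date that normally falls in or after the next line of therapy. Under both readings, next-line time is attributed to the study drug. Only under the literal reading are later events lost, the definition contradicted and PFS biased upward.

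Under that reading, with exponential times and a median PFS of 4 to 6 months, the excess in 12-month PFS is about 1 to 2 points at 5% switching and about 3 to 10 points at 10 to 20%. The documents give no switch rate, so the actual size is unknown. It would be unsafe to conclude that reported PFS must be inflated, or that the design is undermined: the sign depends on the reading, and the sample sizes in section 3.3 are unaffected. The consequence is confined to PFS estimates and to the subgroup and sequence comparisons that use them.

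**What to change.** Replace the censoring sentence in section 2.3 so that:

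- patients who start a new line without progression are censored at the last assessment showing no progression on or before the start of that line, or at the new-line start date if assessment dates were not collected;
- last follow-up is used only for event-free patients with no new line.

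Add a sensitivity analysis in which progression or death after the switch counts as an event at its actual date. This also addresses possible informative censoring at the switch.

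The cost is a short change of wording plus data work. Section 4 lists treatments among the items collected but mentions neither next-line start dates nor tumour-assessment dates, so centres may have to extract these from the charts. Reported PFS may be slightly shorter than under the literal rule.
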